##### 1. Weight Gain Prevention Intervention

There have been several successful behavioral trials that targeted weight control and/or nutritional modification for the control of Blood Pressure including the multi-center clinical trial TONE; Trials of Nonpharmacologic Interventions in the Elderly. The Weight Gain Prevention intervention used in this study was derived from the Weight Loss Only program developed for TONE. The focus of the intervention will be on preventing weight gain following smoking cessation. Because participants will enter the study at a wide range of body weights, the emphasis will be on preventing the weight gain that accompanies quitting smoking rather than weight loss per se. Each participant will be provided with a copy of The CalorieKing Calorie, Fat & Carbohydrate Counter 2007 Edition, published by Dietclub.

Participants will be advised to engage in 30 minutes or more of moderate intensity activity on most, and preferably all, days of the week. Moderate intensity activities include those that range from 3.0 to 6.0 METS, or 4 to 7 kcal x minute-1. Examples include brisk walking, cycling at moderate speed, and general household cleaning. Participants will be given flexibility in both the specific types of moderate activity they choose to engage in, as well as the method in which they choose to accumulate their activity over the course of the day (e.g., several short bouts of activity vs. a single 30-minute period of exercise).

The Weight Gain Prevention intervention will consist of five individual and 12 group sessions lasting 30-60 minutes conducted over a 12-week period. Sessions will be held in person, but can be made up over the phone if the participant is unable to attend a session. As noted above, the intervention is modeled after the TONE Weight Loss Only protocol. The group sessions, which are largely didactic in format but also include group discussion, address a variety of proven weight management strategies including nutrition education, behavioral skills training, problem solving, "relapse" prevention, and moderate increases in physical activity. Participants also will be instructed to self-monitor their dietary intake and physical activity as a means of gaining additional insight into their behavior patterns, as well as to evaluate success in meeting behavioral goals.

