Each of the individual sessions will focus on reviewing participants' success with meeting dietary, physical activity, and weight goals, and problem solving strategies for increasing adherence and success. Consequently, these sessions will provide more specific, individualized instruction tailored to the needs of each individual participant.

At each session a small snack will be provided to the participants, prepared by the bionutrition department of the General Clinical Research Center (GCRC). The snacks will be designed to be low calorie, nutrient dense, and will illustrate the principles of what is being discussed at the intervention.

At all sessions, tobacco use status, serious adverse event information, and weight will be recorded. At the individual sessions, the participant will be asked about concomitant medications (smoking cessation, weight management, and blood pressure medications only), followed by an expired air carbon monoxide (CO) assessment, and a blood pressure reading. The weight gain prevention intervention portion of the study including 12 group sessions and 5 individual sessions will take approximately 17 hours to complete.

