As with the Weight Gain Prevention the primary rationale for incorporating increases in physical activity is for the weight controlling effects (Blair, 1993; Grilo et al., 1993). However, studies also have demonstrated hypotensive benefits from physical activity that are independent of weight loss (Arroll & Beaglehole, 1992; Whelton et al., 2002). Thus, physical activity appears to provide multiple benefits in terms of BP control, and will comprise an important component of the intervention. Because several studies have shown strength training to be effective at reducing BP (see Kelly & Kelly, 2000 for review), participants also will be encouraged to engage in resistance training as well as aerobic activities. Participants will be given flexibility both in the specific types of moderate activity they choose to engage in, as well as the method in which they choose to accumulate their activity over the course of the day (e.g., several short bouts of activity vs. a single 30-minute period of exercise).

The BP Control Intervention will consist of five individual and 12 group sessions lasting 30-60 minutes conducted over a 12-week period. Sessions will be held in person, but can be made up over the phone if the participant is unable to attend a session. As noted above, the intervention will be modeled after the TONE Weight Loss + Sodium Restriction protocol. Individual sessions will focus on reviewing participants' success with meeting treatment goals and problem solving strategies for increasing adherence and success. Consequently, these sessions will provide specific, individualized instruction tailored to the needs of each participant. The group sessions will address a variety of proven educational and behavioral strategies for modifying diet and physical activity. Several of the intervention components involve strategies similar to those included in the smoking cessation intervention (e.g., self-monitoring, problem solving, relapse prevention). Attempts will be made to emphasize these similarities and to build on previous mastery experiences as a means of promoting continuity across intervention components and enhancing self-efficacy.

At each session a small snack will be provided to the participants, prepared by the bionutrition department of the General Clinical Research Center (GCRC). The snacks will be designed to be low calorie, nutrient dense, and will illustrate the principles of what is

being discussed at the intervention.

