### Follow-up Visits

Two follow-up visits will be conducted at six- and 12-months post cessation. Participants will be asked to return to the Preventive Intervention Center for these visits. The procedures performed at these visits will be largely the same. The participant will be asked to report their current smoking status, followed by an expired air carbon monoxide (CO) assessment. For those who fail the CO test (i.e., CO > 10 ppm), yet still claim to be a nonsmoker, a salivary cotinine test will be given to provide a confirming/disconfirming assessment. For those who fail the CO test but report using a nicotine replacement therapy (which would alter the results of the salivary cotinine

test) will instead be tested for thiocyanate via blood draw.

Vitals will also be taken (weight, pulse, blood pressure and waist circumference). Percentage of body fat will be measured using a bioelectrical impedance analysis. Serious adverse event information, and concomitant medication (smoking cessation, weight management, and blood pressure medications only) will be recorded. Current physical activity level will be assessed using the long version of the International Physical Activity Questionnaire (IPAQ). The participant will also be asked to report on their dietary intake by completing two commonly-used dietary screeners. Percent of energy intake from fat will be assessed using the National Cancer Institute (NCI) Fat Screener. Fruit and vegetable intake will be assessed using the All Day version of the NCI Fruit and Vegetable Screener.

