## **XI.2**

### ***Provide the rationale or power analysis to support the number of subjects proposed to complete this study.***

This study is a multi-site, randomized clinical trial, with study sites in Iowa City, IA, Rochester, MN, and Memphis, TN. The sample size calculations provided below reflect the target number of participants for the entire trial, across each of the three sites. Only subjects that meet criteria for tobacco abstinence at the end of the 4-week smoking cessation phase will be eligible for randomization, and of these participants, only those that meet criteria for prolonged abstinence through 1-year follow-up will be included in the primary analysis. Because methodological factors such as abstinence criteria and length of follow-up can have a significant impact on the primary endpoints, we consulted the extant literature and chose only studies that were fairly similar to the proposed project to obtain estimates for sample-size planning. The majority of these studies present data as change from baseline. For this reason, sample-size calculations for the present investigation are based on an analysis of change scores. However, an alternative to analyzing change scores is to analyze follow-up data using an analysis of covariance model with the baseline value included as a covariate. In addition to adjusting each subject's follow-up score for his or her baseline score, the analysis of covariance approach has the advantage of being unaffected by baseline differences. This approach also typically has greater statistical power to detect a treatment effect than analyzing change scores (Vickers et al. 2001). Therefore, sample-size requirements based on an analysis of change scores will provide similar or greater statistical power for analyses that are performed using an ANCOVA approach.

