Data Analytic Plan

Study Title: Blood Pressure Control in Hypertensive Smokers

NCT: NCT00113074

Approval Date: 09/20/2021

Treatment and Prevention Study Data Analytic Plan

Overview:

The main statistical analyses will be for the three-group randomized clinical trial with the primary analyses restricted to participants that do not relapse to smoking. Participants who discontinue study participation will be assumed to have relapsed to smoking. Therefore, analyses will be restricted to those with available data.

The primary efficacy endpoints are BP and body weight. Since the aim is to evaluate long-term efficacy, the primary analysis will evaluate treatment effects at 1-year. Analyses will also be conducted to assess changes in BP and body weight at six months. The primary analysis will be restricted to participants that have not relapsed to smoking and who provide follow-up data. Secondary analysis will be performed using all participants. The primary analysis will be performed using ANCOVA to assess for treatment effects adjusting for the baseline value of the dependent variable, study site, and any baseline variables found to differ significantly between groups. In all cases, each of the two experimental groups will be compared to the UL group. Since there are two pair-wise treatment comparisons of interest (BPC vs. UL; WGP vs. UL), we will utilize Fisher's least significant difference (LSD) approach to protect against inflation of the experimentwise error rate. An initial omnibus test will be used to test the null hypotheses that all group means are equal. Rejection of the null hypothesis will result in subsequent pair-wise comparisons between treatment groups. Conversely, if the null hypothesis associated with the omnibus test is not rejected, pair-wise comparisons will not be necessary.

Secondary endpoints will include servings of fruits and vegetables per day, dietary fat intake (% of total energy from fat), overnight urinary chloride excretion (mmol/day), and self-reported physical activity (kcal/kg/day). The analyses for the secondary endpoints will be similar to that for the primary endpoints, with groups compared using ANCOVA to assess for treatment effects adjusting for baseline values, study site, and baseline variables found to differ significantly between groups. In all cases, each of the two experimental groups will be compared to the UL group.

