Relapse to tobacco use will be analyzed as an exploratory endpoint. At every contact following randomization subjects will be assessed for relapse to tobacco use, with relapse defined as using tobacco on seven consecutive days or using tobacco at least one day per week on two consecutive weeks. This definition is consistent with that proposed by the Society for Research on Nicotine and Tobacco (Hughes et al., 2003). For subjects that relapse, the date of relapse will be defined as the first day of tobacco use in the 7-day or 2-week period. Subjects that discontinue study participation prior to the 1-year follow-up visit, who have not already met relapse criteria, will be assumed to have relapsed to using tobacco. For these subjects, the date of relapse will be assigned as the day following their last study visit. Time to relapse will be analyzed using Cox proportional hazards regression (PROC PHREG) with time to relapse as the dependent variable and intervention group as the independent variable. For subjects that do not relapse to using tobacco, the time to relapse will be censored as of the date of their 1-year follow-up visit. Additional multivariable analyses assessing characteristics associated with relapse to tobacco use will be considered. However, these analyses will be considered exploratory in nature since our ability to perform meaningful multivariable analyses will be dependent on the number of subjects that relapse to tobacco use.

A number of additional analyses will be performed to describe the study characteristics and assess comparability between study groups. Participant adherence will be assessed as percentage of contacts completed and compared between groups using the rank sum test. The percentage of subjects that use other products (or programs) for smoking cessation, blood pressure or weight control will be summarized separately and compared between intervention groups using Fisher's exact test. Changes in hypertension status will be noted and coded as: -1=decrease in status, 0=no change, +1=increase in status; and changes in hypertension medication status will be noted and coded as: -1=decrease in medication, 0=no change, +1=increase in medication. Using these coded variables, changes in hypertension status and medication status will be compared across treatment groups using the Kruskal-Wallis test.

Analyses for phase 1 (smoking cessation):

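### Relapse is looked for at every contact, and the two active arms have 17 more contacts than Usual Lifestyle, so short recovered episodes in the 12-week session period are more likely to be found there

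*SAP*

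**What the plan says.** The relapse paragraph of the SAP (same text in Protocol XI.1) states: "At every contact following randomization subjects will be assessed for relapse to tobacco use". Relapse means "using tobacco on seven consecutive days or using tobacco at least one day per week on two consecutive weeks". It is labelled an exploratory endpoint and analysed by Cox regression, with dropouts who have not already relapsed counted as relapsing the day after their last visit.

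Relapse also decides who is analysed for blood pressure and weight. The SAP Overview says: "The primary analysis will be restricted to participants that have not relapsed to smoking and who provide follow-up data". Protocol XI.2 says that "only those that meet criteria for prolonged abstinence through 1-year follow-up will be included in the primary analysis". The relapse paragraph holds the only definition of relapse after randomization in either document, although neither document expressly ties it to this exclusion.

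Contact after randomization differs by arm (Protocol VII.E.6):

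- Weight Gain Prevention: "The Weight Gain Prevention intervention will consist of five individual and 12 group sessions lasting 30-60 minutes conducted over a 12-week period". The Blood Pressure Control schedule is the same: "The BP Control Intervention will consist of five individual and 12 group sessions lasting 30-60 minutes conducted over a 12-week period".
- In both arms: "At all sessions, tobacco use status, serious adverse event information, and weight will be recorded". Exhaled CO is measured at the individual sessions only.
- Usual Lifestyle: two self-help books and no sessions.
- All arms: "Two follow-up visits will be conducted at six- and 12-months post cessation". These visits take current smoking status and CO, plus a questionnaire that covers smoking status and quit attempts.
- The cessation program includes four phone calls meant to pick up early relapse, made in its first few months. They are not arm-specific, and their timing relative to randomization is not fixed. Participants who quit on their own skip the cessation portion and so appear to get no calls.

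**The concern.** The relapse definition is sensitive to short episodes: a single week of smoking is enough. Someone in an active arm who smokes for a week and re-quits meets staff during or just after the episode, is recorded as relapsed and leaves the primary analysis. Someone in Usual Lifestyle with the same history may not be asked until a call or the month 6 visit. By then CO is normal and current status is non-smoking, so the episode counts only if it is recalled and reported.

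Two things are at stake. The primary analysis set is formed by a post-randomization exclusion whose sensitivity depends on arm, so the groups compared are not selected alike. And the relapse comparison leans against the interventions even if true relapse is equal. The second matters because section A.3 of the Protocol background raises the possibility that weight-control efforts detract from quitting; unequal detection could produce an apparent signal of that kind. No planned analysis addresses it.

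**Working it through.** **Contacts.** Sessions per active arm: 12 + 5 = 17. With the two common visits, 17 + 2 = 19 against 2 in Usual Lifestyle. If all four calls fall after randomization, 23 against 6. The difference is 17 either way, all within 12 weeks (84 days). After that the schedules are the same.

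**Chance that a contact falls inside an episode** of L days lying wholly within the 84 days. With weekly group sessions (assumption), an active arm always has one for L of 7 or more. Usual Lifestyle has none without calls. If all four calls fall at random in the window, the chance is 1 - (1 - L/84)^4:

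- 7 days: 1 - (77/84)^4 = 29%
- 14 days: 1 - (70/84)^4 = 52%
- 28 days: 1 - (56/84)^4 = 80%

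**The plan's attrition figures** (Protocol XI.2, Anticipated Attrition). 1267 x 0.45 = 570 randomized; 570 x 0.10 = 57 dropouts; 513 retained; 78 relapsers (78/513 = 15.2%); 513 - 78 = 435, or 145 per group, as stated. Per arm at 1:1:1: 190 randomized, 19 dropouts, 26 relapsers.

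**Spurious hazard ratio in the planned Cox model.** Dropouts count as events, so an active arm has 26 + 19 = 45 events in 190 (23.7%). Assume equal true relapse in all arms. Let f be the share of relapses that end in a re-quit, and m the share of those missed in Usual Lifestyle; the active arms are taken to miss none. Neither f nor m is in the documents.

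Missed = 26 x f x m; p_UL = (45 - missed)/190; HR is approximately ln(1 - 45/190) / ln(1 - p_UL).

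| f | m | Missed | UL events | p_UL | HR |
|---|---|---|---|---|---|
| 20% | 25% | 1.3 | 43.7 | 23.0% | 1.03 |
| 30% | 50% | 3.9 | 41.1 | 21.6% | 1.11 |
| 40% | 75% | 7.8 | 37.2 | 19.6% | 1.24 |

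This treats all re-quit episodes as falling in the session period. If only half do (assumption), missed is 0.65, 1.95 and 3.9, and the HR is 1.02, 1.05 and 1.11.

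**Weight.** Missed relapsers stay in the Usual Lifestyle set: 1.3/(145 + 1.3) = 0.9% to 7.8/(145 + 7.8) = 5.1% of it. If they gained 1-3 kg less than abstainers (assumption), the Usual Lifestyle mean falls by 0.009 x 1 = 0.01 kg to 0.051 x 3 = 0.15 kg, against the 2.0 kg that the plan calls clinically meaningful. A harsher case has half of all relapses in the session period and none recalled: 0.15 x 0.5 x 171 = 12.8 missed; 12.8/(145.4 + 12.8) = 8.1%; x 3 kg = 0.24 kg. The planned power for 2.0 kg would then fall from 0.88 to 0.77.

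**The case against.** The case on the other side has five parts, and much of it stands.

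- **Usual Lifestyle is not unobserved.** The four calls exist to find early relapse, and the month 6 and 12 questionnaire asks about quit attempts, which a relapse followed by a re-quit would involve. These narrow the gap. They do not close it: the calls add equally to every arm, their timing is loose, self-quitters appear to have none, and the questionnaire relies on recall over months.
- **The gap is confined to 12 weeks.** Smoking that continues to month 6 or 12 can be found in every arm. A reader might infer unequal detection through the whole year; the visit schedule does not support that.
- **The size is limited.** A reader might work from retained participants only (26/171 per arm) and reach an HR of 1.06-1.47. The SAP does not plan that model. It counts dropouts as events, which dilutes the difference. Group sessions have no CO test, so the active arms will also miss some episodes.
- **Relapse is exploratory**, and its definition is not expressly made the rule for the primary set. But the primary set needs a rule for relapse, and no other one is given.
- **An analysis of all participants is already planned** and is free of this filter. It is secondary, so the primary result still rests on the filtered set.

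A reader might also infer that the primary blood pressure and weight results are invalid on this ground. The calculations do not support that.

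**Conclusion.** The point holds in limited form. The detection rule depends on arm, by 17 scheduled contacts in the 12-week session period, and it bears on short episodes that have ended before month 6. Under the stated ranges for re-quitting and missed episodes, the relapse comparison would show a spurious HR of about 1.03-1.24 (1.11 at 30% and 50%), or about 1.02-1.11 if only half of those episodes fall in the session period. These figures rest on assumptions that the documents cannot confirm, and on perfect detection in the active arms.

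For weight the shift is likely small and, if relapsers gain less, toward no difference. For blood pressure the direction is not established. What is affected most is the between-arm relapse comparison and the claim that the primary sets were selected alike. It is worth correcting because the remedy is cheap and still open: Protocol VII.A.4 says that data collection is complete and only analysis and manuscript preparation remain.

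**What to change.** Amend the SAP relapse paragraph, the SAP Overview and Protocol XI.1, before outcomes are compared by arm if that is still possible.

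1. **Relapse comparison.** Take relapse status from information sought identically in all arms at the 6- and 12-month visits: reported use, the tests done there and the questionnaire. Analyse it as binary or interval-censored. Keep the every-contact Cox model as a sensitivity analysis.
2. **Blood pressure and weight.** Repeat the primary ANCOVA, as a pre-specified sensitivity analysis, in the set defined by common-visit relapse status. Report relapse by arm and by the contact at which it was detected, which would show the actual size of the problem. Making the common-visit rule the only primary rule is harder to defend, because it would return known relapsers to a set that XI.2 defines by prolonged abstinence.

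The detailed visit text specifies only current smoking status. If use since the previous visit was not recorded at months 6 and 12, use the status, tests and questionnaire that were collected and state the limit.

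Cost: SAP wording, one re-derived flag, one repeated model and one table. Exact relapse dates become intervals in the main relapse comparison, and some brief recovered episodes no longer count there.

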Relapse to tobacco use will be analyzed as an exploratory endpoint. At every contact following randomization subjects will be assessed for relapse to tobacco use, with relapse defined as using tobacco on seven consecutive days or using tobacco at least one day per week on two consecutive weeks. This definition is consistent with that proposed by the Society for Research on Nicotine and Tobacco (Hughes et al., 2003). For subjects that relapse, the date of relapse will be defined as the first day of tobacco use in the 7-day or 2-week period. Subjects that discontinue study participation prior to the 1-year follow-up visit, who have not already met relapse criteria, will be assumed to have relapsed to using tobacco. For these subjects, the date of relapse will be assigned as the day following their last study visit. Time to relapse will be analyzed using Cox proportional hazards regression (PROC PHREG) with time to relapse as the dependent variable and intervention group as the independent variable. For subjects that do not relapse to using tobacco, the time to relapse will be censored as of the date of their 1-year follow-up visit. Additional multivariable analyses assessing characteristics associated with relapse to tobacco use will be considered. However these analyses will be considered exploratory in nature since our ability to perform meaningful multivariable analyses will be dependent on the number of subjects that relapse to tobacco use.

A number of additional analyses will be performed to describe the study characteristics and assess comparability between study groups. Participant adherence will be assessed as percentage of contacts completed and compared between groups using the rank sum test. The percentage of subjects that use other products (or programs) for smoking cessation, blood pressure or weight control will be summarized separately and compared between intervention groups using Fisher's exact test. Changes in hypertension status will be noted and coded as: -1=decrease in status, 0=no change, +1=increase in status; and changes in hypertension medication status will be noted and coded as: -1=decrease in medication, 0=no change, +1=increase in medication. Using these coded variables, changes in hypertension status and medication status will be compared across treatment groups using the Kruskal-Wallis test.

Analyses for phase 1 (smoking cessation)

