### **Primary Endpoint: Blood Pressure**

For this endpoint sample-size requirements were determined based on preliminary data from the TONE trial. In this trial the mean change from baseline for the combined Weight Loss plus Sodium Restriction intervention was observed to be -5.3 mmHg (SPB) and -3.4 mmHg (DBP). Effect sizes of similar magnitude have been observed in other studies evaluating lifestyle modification interventions for controlling blood pressure (e.g., Blumenthal et al., 2000; PREMIER Collaborative Research Group, 2003; Singh et al., 1995; Wassertheil-Smoller et al., 1992). From the TONE trial, the pooled estimate of the standard deviation of SBP change from baseline was approximately 14.5 mmHg for SPB and 9.4 mmHg for DBP. Based on these assumed standard deviations, Table 4 lists the sample-size required to provide statistical power of 80% to detect a range of differences between groups with respect to mean BP change from baseline using a two-tailed, alpha=0.025 level test. As can be seen from Table 4, an effective sample-size of 145 per group is required to provide statistical power of approximately 80% to detect

differences between groups consistent with the magnitude of effect observed for the Weight Loss plus Sodium Restriction intervention from the TONE trial.

Table 4. Sample-size for Detecting Difference in Blood Pressure Change from Baseline  
Sample-size requirements for SBP Sample-size requirements for DBP

Difference Between Groups (mmHg)	Standard Deviation (mmHg)	Sample Size	Required per group*	Difference Between Groups (mmHg)	Standard Deviation (mmHg)	Sample Size	Required per group*
5.1	14.5	155	3.1	9.4	176		
5.2	14.5	149	3.2	9.4	166		
5.3†	14.5	144	3.3	9.4	156		
5.4	14.5	139	3.4†	9.4	147		
5.5	14.5	134	3.5	9.4	139		

\* Sample-size required to provide statistical power of 80% using a two-sided, alpha=0.025 level test.

† A difference of this magnitude is consistent with the effect observed for the Weight Loss plus Sodium Restriction intervention from the TONE trial.

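### Change in hypertension status is coded -1/0/+1 and compared by an unadjusted Kruskal-Wallis test; a baseline-adjusted ordinal model would give effect estimates and, under stated assumptions, roughly 5 to 12 points more power for this additional analysis

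*SAP*

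**What the plan says.** The SAP paragraph on additional analyses, repeated in Protocol XI.1, defines the variable: "Changes in hypertension status will be noted and coded as: -1=decrease in status, 0=no change, +1=increase in status". Change in antihypertensive medication gets the same three-level code. The test for both is then given: "Using these coded variables, changes in hypertension status and medication status will be compared across treatment groups using the Kruskal-Wallis test". No covariate, pairwise contrast, effect measure, alpha level or time point is stated. Neither document says which categories make up status. The JNC 7 bands used for eligibility (Protocol VI.13) are the natural reading, and I use them here.

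The paragraph opens by stating its purpose: "A number of additional analyses will be performed to describe the study characteristics and assess comparability between study groups". The efficacy analysis of BP is separate. The SAP Overview specifies an ANCOVA at 1 year, adjusted for the baseline value of the outcome, study site, and baseline variables that differ significantly between groups.

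BP is measured at the randomization visit and at the 6- and 12-month visits (Protocol VII.E.6). Antihypertensive medication, dose and frequency are recorded at entry (Protocol VI.13), and BP medication is recorded again at follow-up.

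**The concern.** The code discards three things: the baseline category, the position within it, and the number of categories moved. Prehypertension to Stage I and prehypertension to Stage II both score +1. Participants at 122 and 138 mmHg start in the same category with very different chances of leaving it, and an unadjusted test treats that difference as noise. Protocol XI.2 itself argues for baseline adjustment in the BP analysis, because of its power and its insensitivity to baseline imbalance. The same reasoning carries over to a category derived from BP.

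Kruskal-Wallis also returns only a test across three groups. A reader who wants to know how far Blood Pressure Control (BPC) or Weight Gain Prevention (WGP) shifts hypertension status relative to Usual Lifestyle (UL) gets no estimate or interval. What is at stake is how informative this one comparison is. The trial's main BP conclusion does not rest on it.

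**Working it through.** **1. The plan's own figure.** Protocol XI.2, Table 4, uses a difference of 5.3 mmHg, an SD of 14.5 mmHg, 80% power and a "two-tailed, alpha=0.025 level test". The normal approximation is

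n = 2 (z₀.₉₈₇₅ + z₀.₈₀)² (SD/difference)² = 2 × (2.241 + 0.842)² × (14.5/5.3)² = 142.3, so 143 per group.

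The two-sample t calculation gives 143.6, so 144, as in Table 4. The plan then works with 145. It gives no power or sample size for hypertension status.

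**2. Why baseline matters to this code.** Take a UL participant with no mean change, a change SD of 14.5 mmHg and a slope of 1 (illustrative assumptions). The chance of reaching 140 mmHg is 1 − Φ(18/14.5) = 11% from 122 mmHg and 1 − Φ(2/14.5) = 45% from 138 mmHg. The unadjusted test sees both participants as the same.

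**3. Simulation of the two analyses.** Inputs from the documents: 145 per group, effect 5.3/3.4 mmHg (systolic/diastolic), change SD 14.5/9.4 mmHg, and category limits 120/80, 140/90 and 160/100.

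Assumed, because the documents do not give them:
- baseline systolic BP (SBP): normal with mean/SD parameters 138/12, 130/12 or 128/8, truncated to 120–160;
- slope β of 1-year on baseline BP: 0.5, 0.75 or 1.0;
- categories from SBP alone, or from SBP and diastolic BP (DBP) with an assumed correlation;
- 145 per group contributing a 1-year category.

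Follow-up SBP = mean + β(baseline − mean) − effect × treatment + error, with error variance 14.5² − (β−1)² × Var(baseline), so that the change SD stays at 14.5. Kruskal-Wallis on the sign of the category change was compared with a likelihood-ratio test from a proportional-odds model of the 1-year category adjusted for baseline BP. Site was not simulated. Each setting had 3,000 simulated trials, and the Monte Carlo standard error of a gain was about 0.6 points.

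BPC against UL, 3 × 3 × 2 = 18 settings at the plan's effect:

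| Two-sided alpha | Kruskal-Wallis | Adjusted ordinal model | Gain in points: range (median) |
|---|---|---|---|
| 0.025 | 63–72% | 71–82% | 5.4–12.3 (8.0) |
| 0.05 | 74–80% | 80–88% | 3.8–9.6 (about 6.6) |

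Variations at alpha 0.025:
- effect 2.65 mmHg: 19.6% to 24.7%, a gain of 5 points;
- effect 8 mmHg: 96.9% to 98.8%, a gain of 2 points;
- baselines down to 100 mmHg, as could occur in treated participants: a gain of 9 to 18 points.

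For the three-group test that the plan names, at alpha 0.05, the gain was about 3 to 13 points. A separate smaller check (300 trials per setting) gave 82% to 87%, 57% to 63% and 76% to 83%.

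Type I error was held by both methods: 4.5–5.3% for the three-group tests at nominal 5%, and 2.4–2.9% pairwise at nominal 2.5%.

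**4. What the gain is worth.** Take the midpoint of the Kruskal-Wallis range, 67.5%, and add the median gain of 8 points to reach 75.5%. The equivalent sample-size ratio is [(2.241 + 0.690)/(2.241 + 0.454)]² = 1.18, or about 18% more participants.

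**5. Where it comes from.** In the runs that tracked it, only about 4% of simulated participants moved more than one category. Losing the number of steps therefore affects few people.

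**The case against.** The strongest reply is that this analysis was never meant to carry efficacy. It sits with adherence and use of other products, and has no alpha or power target. The plan also already contains a better BP analysis: in the same simulations the ANCOVA of continuous BP had about 78–87% power (pairwise, alpha 0.025). That stands, and it limits the point to an optional improvement. It does not remove the point, because this is still a formal between-arm test of a BP outcome, and it gives no estimate.

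Two further objections stand in part. The sentence also covers medication change, for which no ordered 1-year category exists, so the BP-category model cannot be carried over. A status model also does not account for changes in antihypertensive treatment, though neither does Kruskal-Wallis; the two results need to be read together. And the protocol reports data collection complete, so swapping a prespecified test now invites a charge of post hoc choice. The fix has to deal with that.

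Some stronger readings are tempting but not supported:
- A reader might infer that the SAP contradicts itself, since it says "In all cases, each of the two experimental groups will be compared to the UL group". That sentence belongs to the paragraphs on primary and secondary endpoints. For this analysis the plan asks only for a comparison across groups.
- A reader might infer that every other BP analysis adjusts for baseline and site. Covariates are stated for the primary ANCOVA, but not explicitly for the six-month BP analysis or for the secondary analysis in all participants.
- A reader might take a single power gain as a property of the plan. It depends on assumptions that the documents do not settle.

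**Conclusion.** The point holds as a minor improvement to an additional analysis. The planned test is valid and holds its type I error, but it uses less of the data than it could and gives no effect size. With the plan's 145 per group, 5.3 mmHg and SD of 14.5 mmHg, the adjusted ordinal model gains roughly 5 to 12 points of power at two-sided alpha 0.025, with a median of about 8. The gain is about 4 to 10 points at pairwise alpha 0.05, and about 2 at an 8 mmHg effect. These figures rest on assumed baseline distributions and slopes, and on JNC 7 bands as the definition of status. The direction was the same at every non-null setting. The primary BP result and its sample size are unaffected.

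**What to change.** **Hypertension status.** Analyse the 1-year JNC 7 category (normal, prehypertension, Stage I, Stage II) with a proportional-odds model on treatment, baseline SBP and DBP, and study site. Report odds ratios with 95% confidence intervals for BPC against UL and WGP against UL. Keep the -1/0/+1 table as description.

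**Medication change.** Fit an ordinal model to the -1/0/+1 code itself, adjusted for baseline antihypertensive use and site.

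**Timing.** Write and date the change before this comparison is run. If it has already been run, keep the Kruskal-Wallis result as the prespecified one and report the model beside it, labelled supplementary and post hoc.

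**Cost.** A few sentences in the SAP, two models, a check of proportional odds, and the awkwardness of a late change to a prespecified side analysis. No new data are needed.
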